#### 7.2.8.3 Overdosage

The maximal dose of study drug should not be exceeded during the study. Overdose that occurs during the study will be treated and documented as an AE/SAE if it fulfills the criteria. If the overdose does not result in an AE, it should be reported in written form to the designated individual(s) who receive SAE notification. The information contained therein should include study site identification, reporter identification, patient identification, IP, dose, action taken (e.g., supportive measures or therapy), and any comments.

As with any overdose, patients should be monitored closely and observed for expected and unexpected clinical and laboratory effects.

No specific antidote to oxytocin exists, so treatment should be directed at supportive care.

# 7.2.8.4 Abuse Potential

Although no indications of abuse have been reported, oxytocin will still be monitored for abuse or misuse.

#### 8 STUDY ACTIVITIES

# 8.1 Screening Visit 1

## **Informed Consent**

Before the potential participant has undergone any study-related Screening procedures, including any down-titration or withdrawal of medications, the nature of the study and the potential risks associated with it will be explained to the patient, and the patient will be given an opportunity to ask questions to his or her satisfaction. After the questions are answered, but before proceeding further, the patient must read and sign a written informed consent form. This signed informed consent form will be retained in the investigator's study file, and the date the patient signed the form will be entered into the CRF. The patient will be provided with a copy of his or her signed and dated informed consent form.

After providing written informed consent, patients will be assessed for study entry eligibility.

# Screening Assessments and Procedures:

- 1. Obtain written informed consent to participate
- 2. Inclusion/exclusion criteria
- 3. Demographics
- 4. Confirm chronic migraine diagnosis
- 5. Medical, neurological, and medication history
- 6. Physical examination
- 7. Nasal cavity examination
- 8. Vital signs
- 9. 12-lead ECG
- 10. Clinical laboratory tests (hematology, standard blood chemistry panel, TSH, HbA1C, and urinalysis)
- 11. Serum pregnancy test (for women of childbearing potential [WoCBP]) processed at central lab
- 12. Urine drug test
- 13. "Screening/Baseline" version of the C-SSRS. Any patient exhibiting Type 3, 4, or 5 suicidal ideation in the last 6 months or who has had suicidal behavior in the last 12 months should be deemed a screen failure and assessed for appropriate follow-up care. Results of the C-SSRS should be reviewed to ensure the patient is not experiencing suicidal ideation or has had suicidal behavior that requires emergency intervention
- 14. MSI-BPD
- 15. Placebo response training

16. Provide the patient with the e-diary training. Reminder notifications for diary completion should be set up in the IRT and in the ePRO app according to the patient's preferences

During this Screening/Wash-Out/Run-In Period, if any test results come back and indicate a patient's ineligibility for the study, the patient should be considered a screen-failure (SF) and informed that they are not eligible for the study and can stop completing the e-diary. However, if the investigator determines that the patient should be brought back into the clinic for re-testing, the patient should continue completing the e-diary until a final determination regarding eligibility is made.

In addition, any patients not meeting the randomization criteria will be considered a SF.

Only those patients meeting all the inclusion and none of the exclusion criteria will be eligible to continue.

# 8.2 Baseline/Randomization Visit 2 (Day 1)

If the patient meets randomization (randomization will be stratified by study site and concomitant migraine preventive medication) criteria, the patient will be authorized to continue in the study, will undergo several Baseline assessments at this visit, and will be randomized via the randomization system to receive double-blind study drug. If the patient does not satisfy randomization criteria, the patient has failed to qualify for this study and should be considered an SF, with the reason documented. There is no requirement for a follow-up visit for SFs; however, the investigator should advise patients who have washed off of medications for the study on next steps of treatment.

If the patient meets randomization criteria, the following procedures will be completed at V2:

- Eligible patients will be randomized in a 1:1:1 ratio to one of 3 treatment arms (A, B or C) as summarized in Section 5.2. Randomization will be stratified by study site and concomitant migraine preventive medication.
- The patient should also be provided with the opportunity to sign a separate consent form for the optional pharmacogenomics blood draw and analysis. Participation in this optional portion of the study is not required. Ideally, the blood drawn for the optional pharmacogenomics should be drawn at the Baseline visit; however, it can be drawn at a subsequent visit if needed. A patient can decide to decline the optional pharmacogenomics but still participate in the main study.

The following assessments and procedures are scheduled for this visit in the following general order:

- Confirm patient's eligibility.
- Review completed diary data with the patient. Provide re-training.

- Update medical history (if any new information has been provided since the Screening Visit).
- Assess occurrence of AEs.
- Assess changes in medication history and concomitant medications.
- Conduct a physical examination, including vital signs and weight.
- Conduct a nasal cavity examination.
- Conduct a 12-lead ECG
- Obtain clinical laboratory tests (standard blood chemistry panel and urinalysis)
- Perform urine pregnancy test (for WoCBP)
- Obtain blood sample for optional pharmacogenomics (after the separate ICF has been signed for pharmacogenomic substudy) if not drawn at a prior visit
- Administer the "Since Last Visit" version of the C-SSRS. Any patient exhibiting Type 3, 4, or 5 suicidal ideation or any suicidal behavior since the Screening Visit should be screen-failed and assessed for appropriate follow-up care. Results of the C-SSRS should be reviewed to ensure the patient is not experiencing suicidal ideation or has had suicidal behavior that requires emergency intervention.
- Have the patient complete placebo response training.
- Administer the HADS: Hospital Anxiety and Depression Scale
- Have the patients complete the following rating scales:
  - 1. MIDAS: Migraine Disability Assessment questionnaire
  - 2. MSQ: Migraine-Specific Quality of Life Questionnaire v2.1
  - 3. CSFQ-14: Changes in Sexual Functioning Questionnaire Short-Form
- Verify patient's ability to use an intranasal device prior to leaving the clinic at Baseline/Randomization/Visit 2. Patient will also take their first study drug dose before leaving the clinic.
- Once it has been confirmed that the patient remains eligible, randomize patient via interactive response technology (IRT) Randomization System
- Dispense 2 unopened nasal applicators of double-blind study drug as assigned via the IRT (one is marked "MORNING" and the other is marked "EVENING"). Prime the two study drug bottles. Supervise the patient as they take one dose of study drug from the appropriate study drug bottle (AM or PM) depending on appointment time.
- Each treatment bottle number should be recorded in the patient's records. Review patient instructions regarding study drug dosing and diary completion

# 8.3 Visits 3 (Week 4) and 4 (Week 8)

Visits 3 and 4 are similar study visits that are scheduled to be conducted after 4 weeks, and 8 weeks of treatment, respectively. The following assessments and procedures are scheduled for both of these visits in the following general order:

- Assess changes in medication history and concomitant medications
- Assess occurrence of AEs
- Conduct nasal exam cavity examination
- Obtain vital signs
- Conduct a12-Lead ECG
- Obtain clinical laboratory tests (standard blood chemistry panel and urinalysis)
- Perform urine pregnancy test (for WoCBP).
- Obtain blood sample for optional pharmacogenomics (after the separate ICF has been signed for pharmacogenomic substudy) if not drawn already at a prior visit
- Have the patient complete placebo response training.
- Administer the "Since Last Visit" version of the C-SSRS. Results of the C-SSRS should be reviewed to ensure the patient is not experiencing suicidal ideation or has had suicidal behavior that requires emergency intervention
- Have the patient complete:
  - 1. PGIC: Patient Global Impression of Change
  - 2. HADS: Hospital Anxiety and Depression Scale
  - 3. MSQ: Migraine-Specific Quality of Life Questionnaire v2.1
- Review completed diary data and diary compliance with the patient. Provide re-training.
- Assess study drug compliance and collect previously dispensed study drug and bottles
- Dispense 2 unopened nasal applicators of double-blind study drug as assigned via the IRT (one is marked "MORNING" and the other is marked "EVENING"). Prime the two study drug bottles.
- After all the assessments at each visit have been completed, the patient should be given an appointment to return to the clinic for the next scheduled visit, and be re-instructed, as necessary, in the completion of the diary, dosing instructions, and reminded to bring study drug back to the clinic at their next visit.

# 8.4 Visit 5 (Week 12) or Early Termination Visit

Visit 5 should occur after 12 weeks of double-blind study drug treatment. At this visit, the patient will return all study drug. The following assessments are completed:

- Assess changes in medication history and concomitant medications
- Assess occurrence of AEs
- Conduct a physical examination, including vital signs, weight
- Conduct a nasal cavity examination
- Conduct a 12-lead ECG
- Obtain blood for clinical laboratory tests (hematology, standard blood chemistry panel, urinalysis)
- Perform in-clinic urine pregnancy test (for WoCBP)
- Obtain blood sample for optional pharmacogenomics (after the separate ICF has been signed for pharmacogenomic substudy) if not drawn at a prior visit
- Have the patient complete placebo response training
- Administer the "Since Last Visit" version of the C-SSRS. Results of the C-SSRS should be reviewed to ensure the patient is not experiencing suicidal ideation or has had suicidal behavior that requires emergency intervention
- Have the patient complete:
  - 1. PGIC: Patient Global Impression of Change
  - 2. HADS: Hospital Anxiety and Depression Scale
  - 3. MIDAS: Migraine Disability Assessment questionnaire
  - 4. MSQ: Migraine-Specific Quality of Life Questionnaire v2.1
  - 5. CSFQ-14: Changes in Sexual Functioning Questionnaire Short-Form
- Review completed diary data and diary compliance with the patient. Provide re-training as needed.
- Assess study drug compliance and collect previously dispensed study drug and bottles
- After all the assessments at each visit have been completed, the patient should be given an appointment to return to the clinic for the Follow-up visit.

All patients who withdraw early from the study will be encouraged to complete the ET Visit for safety evaluations (Visit 5) within 7 days from withdrawal of study, followed by a Safety Follow-up Visit (Visit 6) approximately 14 days from the last study drug administration.

# 8.5 Visit 6 (Week 14)/Safety Follow-up

Visit 6 (Week 14) or Safety Follow-up in-person visit will occur 14 days after the final treatment (Visit 5).

The following assessments are completed:

- Assess AEs
- Conduct nasal exam, only if there is any ongoing or new AE of the nasal cavity
- Conduct vital signs
- Obtain samples for clinical lab tests (hematology, blood chemistry, and/or urinalysis), only if there are any clinically significant findings from the V5 labs
- Perform in-clinic urine pregnancy test (for WoCBP)
- Optional blood draw for pharmacogenomics (after the separate ICF has been signed for pharmacogenomic substudy) if not drawn at a prior visit
- Administer the "Since Last Visit" version of the C-SSRS. Results of the C-SSRS should be reviewed to ensure the patient is not experiencing suicidal ideation or has had suicidal behavior that requires emergency intervention

# **8.6** Early Termination (After Randomization)

In accordance with the Declaration of Helsinki, patients have the right to withdraw from the study at any time for any reason, and they will be advised of this right. The investigator and Tonix also have the right to remove patients from the study. Specific reasons for removal of a patient from the study could include, but are not limited to:

- An AE
- An illness that, in the judgment of the investigator or Tonix, might invalidate the study data or place the patient at risk
- The request of the patient, investigator, or Tonix, whether for administrative or other reasons
- Pregnancy

Patients who wish to terminate their participation in the study should be instructed to come to the clinic for an ET Visit. The purpose of the ET Visit is to obtain critical information about the patient's participation and should be scheduled preferably before there has been a substantial lapse in study drug usage. However, even if there has been a drug lapse, the

patient should be encouraged to return to the clinic for this visit and should be instructed to return all study drug and bottles. Additionally, the patient should be encouraged to also subsequently attend the Safety Follow-Up Visit (Visit 6). NOTE: These visit procedures are not intended for patients who fail to qualify for randomization or for patients who withdraw from the study prior to receipt of a dose of double-blind study drug.

In addition to documenting the reason for ET during the ET visit, assessments and procedures should be completed according to the V5 schedule. For the Safety Follow-Up Visit (Visit 6), assessments and procedures should be completed according to the V6 schedule.

# 9 QUALITY CONTROL AND ASSURANCE

Unless otherwise specified, procedures, data collection and evaluation will be conducted as per the standard operating procedures of the CRO. The investigator will assume the responsibility of ensuring the completeness and accuracy of the clinical data. All data will be verified for quality control and will also be patient to audits from Tonix or designee to ensure quality.

#### 10 PLANNED STATISTICAL METHODS

# **10.1** General Considerations

All safety and efficacy data will be listed and summarized. Unless otherwise specified, Baseline is defined as the last observed measurement, whether scheduled or unscheduled, prior to study drug administration. Safety and efficacy endpoints will be summarized by treatment group. Continuous variables will be summarized using the number of patients with data (n), mean, SD, median, minimum, and maximum. Selected continuous variable summaries will also include the standard error. Categorical variables will be summarized using frequency counts and percentages. All values summarized will also be presented in listings.

The statistical analysis plan (SAP) will provide further details for statistical methodology.

All analyses will be performed using SAS® version 9.4 or higher, unless otherwise specified.

#### 10.1.1 Estimand

The primary efficacy endpoint is defined as the change in monthly migraine days from Baseline (last 28 days prior to randomization) to month 3 (last 28 days of treatment). For defining months, diary days will be divided into 28 day "months"; Days 1 to 28 will be Month 1; Days 29 to 56 will be Month 2; and Days 57 to 84 will be Month 3. The change in count of days with migraine vs the baseline will be compared between treatment groups.

The target population is all patients in the mITT population with CMs as defined by the inclusion/exclusion criteria.

A "while on treatment" policy strategy will be used for all intercurrent events. That is, the data will be considered independently from any intercurrent event, such as rescue medication usage and study discontinuation. The approach for partial and missing data is described in Section 10.1.3.

The population-level summary will be the model-based least-squared means for each arm and differences between treatment arms (analyzed as randomized) at month 3.

## 10.1.2 Multiple Comparisons

A multiplicity algorithm will maintain an overall alpha level of 0.05 across the two dose groups as well as the primary endpoint of change in monthly migraine days from Baseline to month 3, using the graphical method. Full details will be specified in the SAP.

# 10.1.3 Missing Data

Every effort will be made to retain patients in the study; however, patients are free to withdraw from the study at any time for any reason. Patients that withdrawal early will be

asked to return to the clinic for an Early Termination Visit for completion of assessments (see Schedule of Assessments

).

The monthly migraine count will be calculated for patients that have at least 14 days of non--missing data for a given month. For patients with less than 28 days of data, the counts will be normalized to 28 days by taking 28\* [migraine count] / [days of non-missing data].

If less than 14 days are available for a month, then the month will remain missing, but the patient's other months will contribute to the estimation via a mixed-effects model of repeated measures. The mixed model repeated measures analysis will provide unbiased estimates under the assumption that data are missing at random (MAR). Sensitivity analyses will confirm the robustness of the results to deviations from this assumption.

For responder analyses using the monthly migraine days, the values as imputed above will be utilized. If a month is missing, then the patient will be considered a non-responder for that month.

For other responder analyses, patients with missing values will be treated as non-responders.

# **10.2** Determination of Sample Size

The planned total number of randomized patients is approximately 300 and will be randomized 1:1:1 to TNX-1900 30 IU QAM, placebo QPM: TNX-1900 30 IU BID: or placebo BID. The sample size estimate was derived using a two-sided t-test with 90% power and 5% two-sided significance level to test the primary efficacy statistical superiority hypothesis of TNX-1900 30 IU BID over placebo.

Based on a post-hoc analysis of a chronic migraine subgroup from a prior study, it is anticipated that a difference in mean change from Baseline to study end (last 28 days of double-blind) in migraine headache days between TNX-1900 30 IU BID and placebo BID would be approximately 1.84 with a common standard deviation of  $\pm$  3.95. As such the required sample size per group is approximately 100.

Accounting for the multiplicity adjustment by applying an alpha of 2.5% to the first test yields power of approximately 85% with the above assumptions.

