## Safety Follow-up Period (Visit 6)

Approximately 14 days (+4 days) after Visit 5 or End of Treatment (ET), all randomized patients will attend a Safety Follow-up Visit.

A schema of the study design is provided in Figure 1.

Figure 1 **Study Schema** Arm A: N=100 TNX-1900 30 IU QAM / Placebo QPM Subjects with Arm B: N=100 Chronic TNX-1900 30 IU QAM / TNX-1900 30 IU QPM Migraine Arm C: N=100 Placebo QAM / Placebo QPM Completion of Randomization Treatment N=300 Est N=265 Visit 1 Visit 2 Visit 5/ Visit 6 Visit 3 Visit 4 Randomization Screening ET Safety Follow-up Entry 28-day Run-In Criteria Baseline 84-day Double-Blind Treatment 0-21 days

Week 8

Week 12

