## 10.7.2 Efficacy Analysis

#### 10.7.2.1 Primary Efficacy Analysis

Summary statistics (mean, SD, median, minimum, maximum) for the primary efficacy endpoint will be reported for the change from the Baseline to month 3 for each of the treatment groups. The change from Baseline will be analyzed in a Mixed-Effects Model of Repeated Measures (MMRM) model with fixed effects of treatment, month, baseline value, treatment by month interaction, baseline by month interaction, site, and stratification factor (preventive medication use); an unstructured covariance matrix will be used. Least square means (LSMs), standard errors, and the LSM differences (each treatment vs placebo) will be reported for each month. Denominator degrees of freedom will use the Kenward Rogers approach. Should the model fail to converge, heterogeneous Toeplitz, heterogeneous first-order autoregressive, Toeplitz, first order autoregressive and compound symmetric will be attempted in that order; in these cases, the sandwich estimator (Diggle and Kenward 1994) will be used to estimate the standard errors of the fixed effects parameters and the denominator degrees of freedom will utilize the DDFM=BETWITHIN option in SAS®.

To account for the blinded interim sample size re-estimation (Section 10.8), data from the interim and post-interim cohorts will be combined using the inverse normal method to test

the null hypotheses that there is no difference in the change from Baseline to month 3 in number of migraine days per month between each of the active groups and placebo (Cui et al 1999):

$$Z_1 = \Phi^{-1}(1 - p_1)$$
 (1)  
and  $Z_2 = w_1 Z_1 + w_2 \Phi^{-1}(1 - p_2)$ 

Where:

 $Z_1$  = the Z statistic for the first stage

 $Z_2$  = the combination test statistic at the end of the second stage

wi = the weighting applied for each associated Z statistic

 $p_1$  = the first stage p-value

p2 =the second stage p-value based on second stage participants

The weights are defined prospectively according to the square-root of the planned proportion of participants in the two stages, relative to the preplanned total enrollment of 300 participants, as  $w_i = \sqrt{0.5}$ . In order to control the type-I error, adaptive changes of the stage wise sample sizes will not lead to changes of the weights (Lehmacher and Wassmer 1999).

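### Protocol 10.2's 90% and about 85% power assume that essentially every randomised patient has a Month 3 value, which 10.2 does not say and which does not fit Figure 1's apparent estimate of 265 completers out of 300

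*Protocol*

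**What the plan says.** Protocol 10.2 plans about 300 patients, randomised equally to three arms. "The sample size estimate was derived using a two-sided t-test with 90% power and 5% two-sided significance level", for 30 IU BID against placebo. The assumed difference in mean change is 1.84 migraine headache days with a common SD of 3.95, taken from a post-hoc subgroup of a prior study. The section concludes: "As such the required sample size per group is approximately 100". For multiplicity it adds that "applying an alpha of 2.5% to the first test yields power of approximately 85% with the above assumptions". It does not mention dropout or evaluability.

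The study schema (Figure 1, protocol 3.1) carries the text "Randomization Treatment N=300 Est N=265", directly after the words for completion. The layout was lost when the figure was converted to text, but the natural reading is 300 randomised and an estimated 265 completing treatment.

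Three other provisions decide what a non-completer contributes:

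- Protocol 10.1.1 fixes the primary time point: "Days 57 to 84 will be Month 3".
- Protocol 10.1.3 sets the evaluability rule: "The monthly migraine count will be calculated for patients that have at least 14 days of" non-missing diary data in that month. Otherwise the month stays missing, but the patient's "other months will contribute to the estimation via a mixed-effects model of repeated measures".
- Protocol 10.7.2.1 specifies an MMRM with "fixed effects of treatment, month, baseline value, treatment by month interaction, baseline by month interaction", plus site and preventive medication use. SAP 9.1.2 keeps the baseline value in the model.

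The power text of SAP 8.1.6 is redacted.

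**The concern.** The number that 10.2 calls required and the number it randomises are the same, so nothing is set aside for patients without a Month 3 value. The same protocol appears to expect 35 of 300 patients (11.7%) not to complete.

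The alpha 0.025 figure matters most, because SAP 8.1.5 tests the stronger of the two dose comparisons at that level first. If about 85% is really about 80%, the type II error for that test is about 20% rather than 15%. Anyone interpreting a null or borderline result will rely on the stated power and should know which number of patients it refers to.

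**Working it through.** **Inputs.** From protocol 10.2: difference 1.84, SD 3.95, two-sided t-test, alpha 0.05 and 0.025, 100 per arm. From Figure 1: 265 completers. Assumed: an equal split across arms, and every correlation below.

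**Formula.** With n per arm, the noncentrality is λ = 1.84 / (3.95 × √(2/n)) on 2n − 2 degrees of freedom. Power is the probability that a noncentral t variate exceeds the two-sided critical value in absolute size.

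**Step 1: reproduce the plan.** At n = 100, λ = 1.84 / (3.95 × 0.1414) = 3.29, and power is 90.6% at alpha 0.05 and 84.9% at alpha 0.025. Both stated figures reproduce. The smallest n for 90% at 0.05 is 98 (97 gives 89.8%); for 85% at 0.025 it is 101. So the first figure has two patients per arm to spare and the second has none.

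**Step 2: use the completion estimate.** 265 / 3 = 88.3 per arm, so λ = 1.84 / (3.95 × √(2/88.3)) = 3.10. Power is 86.8% and 79.7%. The equal split matters little: arms of 83 and 93 give 86.6% and 79.4%.

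**Step 3: completing is not the same as having a Month 3 value.** The mismatch works both ways.

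- Some of the 11.7 non-completers per arm may stop late enough to have 14 diary days in Month 3. If 25%, 50% or 75% of them do, n is 91.2, 94.2 or 97.1, and power is 87.9%, 88.9% or 89.8% (alpha 0.05) and 81.1%, 82.5% or 83.7% (alpha 0.025).
- Some completers may have fewer than 14 such days. If 5% do, n = 88.3 × 0.95 = 83.9, and power is 85.1% and 77.4%.

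**Step 4: credit Months 1 and 2 through the MMRM, without baseline.** Spread the non-completers equally over 0, 1 and 2 observed months, and assume the same correlation between any two months. The generalised least squares information for the Month 3 mean gives an effective n of 90.5 (correlation 0.5) to 93.5 (0.8) per arm. Power is 87.6–88.6% and 80.8–82.2%.

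**Step 5: credit baseline as well.** This applies only if 3.95 is an unadjusted SD of change. If one correlation ρ holds across baseline and all months with equal variances, adjusting for baseline reduces the SD to 3.95 × √((1 + ρ)/2). The non-completers are spread as in step 4.

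| ρ | Adjusted SD | Power, alpha 0.05 | Power, alpha 0.025 |
|---|---|---|---|
| 0.5 | 3.42 | 94.7% | 90.8% |
| 0.8 | 3.75 | 90.6% | 84.9% |
| 0.9 | 3.85 | 89.1% | 82.8% |

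At ρ = 0.8 the model gives back the full-sample t-test figures. Below that it exceeds them, and above it falls short.

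**The case against.** The strongest reply is that the trial will not run a completers-only t-test. A patient enters the primary analysis with a single evaluable month, other months contribute, and baseline is a covariate. Step 5 shows that this model can recover the whole loss and more. That stands: a reader might infer that the trial's real power is 80%, and the documents do not support that. Nor do they support the opposite conclusion. They give no correlation and do not say whether 3.95 is already adjusted for baseline. If it is, the baseline gain disappears and step 4 is the better guide.

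A reader might also infer that 10.2 contains an arithmetic error. It does not; its figures follow from its inputs. Nor are 87% and 80% the worst case, since completers with sparse diaries would lower them further (step 3).

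Two further replies have some force. The 265 comes from figure text that lost its layout, and no sentence elsewhere gives a completion rate, so it is a natural reading rather than a stated planning assumption. And this is a Phase 2 proof-of-concept trial whose planning figures are given as approximate, so a gap of 3 to 5 points is modest.

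Protocol 10.8 did provide an interim look that could have raised the sample size. SAP 12 says no interim analysis will be performed, so it no longer serves as a safeguard. The SAP's list of changes to the protocol analyses is redacted, so any explanation there cannot be seen.

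**Conclusion.** The point holds as an unstated assumption of full evaluability that does not fit the protocol's own apparent completion estimate. On the t-test that 10.2 names, 265 completers give about 87% rather than 90% at alpha 0.05, and about 80% rather than 85% at alpha 0.025. This rests on the natural reading of Figure 1, an equal split across arms, and completion standing in for a Month 3 value.

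A shortfall is shown on the stated t-test basis only. For the planned MMRM, the assumed scenarios in steps 4 and 5 run from about 88% to 95% at alpha 0.05 and from about 81% to 91% at alpha 0.025, so they fall on both sides of the stated figures. The documents therefore do not show that the planned analysis is underpowered, and they give no basis for asking for more patients. The finding is limited to protocol 10.2, because the SAP's power text cannot be read.

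**What to change.** Restate protocol 10.2 to say:

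- The 90% (alpha 0.05) and about 85% (alpha 0.025) assume 100 evaluable patients per arm at Month 3.
- With the expected 265 completers, about 88 per arm, the same t-test gives about 87% and 80% for BID against placebo.
- If a higher figure is claimed through the MMRM, the month-to-month and baseline correlations it assumes, and whether 3.95 is an unadjusted SD.

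SAP 8.1.6 needs a matching change only if its redacted text repeats the figures without the assumption. The cost is a few sentences. No test, alpha level, analysis population or enrolment target changes.
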